6.5 Pharmacokinetic Assessments

During the MAD phase 1b (all sites) and POC phase 2 (select sites only) parts of the study, blood samples for PK analysis of BOS161721 or placebo concentration will be collected according to Table 4 and Table 1.

Plasma concentrations of BOS161721 will be measured using a validated immunoassay. The PK parameters will be calculated from the plasma concentration actual time profiles.

6.6 Pharmacodynamic Assessments

Blood samples for PD parameters (plasma) will be collected at times indicated in the Schedule of Assessments (Table 1 and Table 4) for each of the following parameters:

- pSTAT3 (predose [trough] samples only phase 1b)
- Antibodies: CCI [REDACTED]
- Plasma complement (CCI [REDACTED])
- Plasma CCI [REDACTED] and CCI [REDACTED]
- Whole blood for leukocyte immunophenotype (for MAD patients only)

6.7 Pharmacokinetic/Pharmacodynamic Relationship

Evidence of any PK/PD relationships will be evaluated between BOS161721 plasma concentrations and the available PD endpoints and biomarkers.

6.8 Protocol Deviations

Protocol deviations will be documented during the study.

7 STUDY DRUG MANAGEMENT

7.1 Description

7.1.1 Formulation

CCI
[Redacted]

CCI
[Redacted]

Additional information regarding dose preparation will be provided in a separate Pharmacy Manual.

7.1.2 Storage

All supplies of BOS161721 or placebo must be stored in accordance with the manufacturer's instructions. BOS161721 or placebo will be stored in a securely locked area, accessible to authorized persons only, until needed for dosing.

Information regarding storage and dose preparation will be provided in a separate Pharmacy Manual.

7.2 Packaging and Shipment

Investigational medicinal products will be supplied by Boston Pharmaceuticals, Inc. Investigational medicinal products will be packaged and labeled according to applicable local and regulatory requirements.

7.3 Dose and Administration

Details of dosing are provided in [Section 3.1](#).

Each unit dose will be prepared by a qualified staff member. The vials of investigational product (IP) will appear identical and will have a "blinded" label on the vials that will state CCI mg or placebo. When the site goes into the IWRS to request the patient kit(s), the IWRS will assign the appropriate number of kits (regardless of assignment to placebo or active treatment) per the dose (i.e., CCI [Redacted]). If a patient is randomized to the placebo arm, they will receive the matching number of kits.

The designated staff member (or designee under the direction of the designated staff member) will dispense BOS161721 or placebo for each patient according to the protocol, randomization list, and Pharmacy Manual, if applicable.

After receiving sponsor approval in writing, the investigational site is responsible for returning all unused or partially used BOS161721 or placebo to the sponsor or designated third party or for preparing BOS161721 or placebo for destruction via incineration.

Further details are found in a separate Pharmacy Manual.

7.4 Accountability

The Principal Investigator or designee is responsible for maintaining accurate accountability records of BOS161721 or placebo throughout the clinical study. The drug accountability log includes information such as, randomization number, amount dispensed, and amount returned to the pharmacy (if any). Used investigational product returned to the pharmacy may be maintained in an ambient condition. Unused product should follow the instructions in the Pharmacy Manual. The used product that is returned should be marked as 'returned' and kept separate from the products not yet dispensed.

All dispensing and accountability records will be available for sponsor review after database lock procedures are completed. During safety monitoring, the drug accountability log will be reconciled with the products stored in the pharmacy.

7.5 Prohibited Concomitant Therapy

Prohibited concomitant medications are discussed in [Section 4.6](#) and [Appendix 4](#) will be listed as protocol violations if taken when not permitted.

7.6 Compliance

Dosing will be performed by trained, qualified personnel designated by the principal Investigator. The date and time of dosing will be documented on each dosing day. Comments will be recorded if there are any deviations from the planned dosing procedures.

8 STATISTICS

The following analyses are planned:

- An IA will be performed during the last cohort of the MAD portion to determine dose selection for the POC part of the study.
- An additional analysis may be performed for the MAD portion of the study when all MAD patients have completed the safety follow-up or withdrawn from the study, and

prior to final analysis. Data from the POC part of the study will be excluded from this additional analysis.

- The final analysis will be performed when all patients have completed the POC safety follow-up or withdrawn from the study.
- Safety analyses will be performed for DMC reviews throughout the study to evaluate dose escalation decisions and accumulating safety data. The frequency and details of the content and format of the safety review meetings will be described in the SAP and/or DMC charter.

All statistical analyses will be performed using Statistical Analysis Software (SAS®) Version 9 or higher.

The following standards will be applied for the analysis unless otherwise specified. Data will be summarized descriptively by treatment and overall for each study portion. For the MAD part of the study, BOS161721 will be summarized overall and by each dose level, and placebo patients from each cohort will be combined. Select parameters may be summarized using patients from both study parts. Statistical testing will be performed on data from the phase 2 portion only.

Continuous data will be summarized using number, mean, standard deviation (SD), 25th and 75th percentiles, minimum, median, and maximum. Categorical data will be summarized by treatment group using frequency tables (number and percentage). Time to event data will be summarized using counts, medians, 25th and 75th percentiles, and standard error. All data will be listed for all patients.

Statistical inference will be based on a 2-tailed test with an overall 0.10 level of significance, unless stated otherwise.

The effects of noncompliance, background therapy use, treatment discontinuations, premature withdrawal from study and covariates will be assessed to determine the impact on the general applicability of results from this study. Exploratory analyses of the data will be conducted as deemed appropriate. Any deviations from the planned analyses will be described and justified in the final integrated CSR.

Protocol deviations and prohibited medications that define medication failures will be fully assigned and documented before database lock and unblinding.

Further details of the analysis, including the handling of missing data, transformations and other data handling procedures will be provided in the SAP.

8.1 Sample Size

Sample size in the phase 1b part of the study is based on operational consideration.

The sample size in the phase 2 portion is based on the primary endpoint, SRI-4 Response at Day 210. Based on efficacy data from a recently completed study with Ustekinumab⁵¹, where the primary endpoint was also SRI-4, the sample size in the phase 2 part of the BOS161721-02 study is set at 96 evaluable patients. In the

Ustekinumab study of 102 patients, a statistically significant difference in SRI-4 response was shown in favor of Ustekinumab (62% of Ustekinumab treated patients achieved SRI-4 response vs. 33% in patients receiving placebo). The Ustekinumab phase 2 study is an appropriate comparator to BOS161721-02 because both studies share the same primary endpoint of SRI-4 response and BOS161721 and Ustekinumab have overlapping mechanisms of action (T follicular helper and Th17 cell biology).

Approximately 110 additional patients will be randomized in a 2:1 ratio to BOS161721 versus placebo to achieve approximately 96 evaluable patients in the FAS of the phase 2 portion. This assumes 14 patients will drop prior to having received treatment or having completed a post-baseline efficacy measure. Enrollment and randomization will be monitored in a blinded fashion and may be increased if needed to ensure at least 96 evaluable patients are randomized into the FAS.

A total of 96 evaluable patients randomized provides 80% power to detect a treatment difference of 29% in SRI-4 response rates at Day 210, based on a targeted 2-sided significance level of 10% and using a 2-sided Pearson's chi-squared test. This assumes a response rate of 62% for BOS161721 and 33% for placebo.

8.2 Statistical Methods

8.2.1 Analysis Populations

The primary efficacy analysis will be based on the FAS, defined as all patients who receive at least 1 dose (partial or complete) of study treatment and have at least 1 evaluable post-baseline efficacy evaluation. FAS analyses will be conducted on the basis of the randomized treatment.

A per protocol (PP) analysis set may be defined to exclude major protocol violations from the efficacy analysis. The PP Population will include all patients from the FAS except those with major violations to the protocol deemed to impact the analysis of the primary endpoint. These violations will be identified based on blinded data prior to study unblinding. PP analyses will be conducted on the basis of the randomized treatment.

Safety analyses will be based on the safety analysis set (SS), defined as all patients who receive at least 1 dose (partial or complete) of study treatment. Safety analyses will be conducted on the basis of actual treatment received.

Pharmacokinetic analysis will be conducted on the PK analysis set, defined as the FAS with sufficient concentration data for the calculation of PK parameters.

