8.2.6 Pharmacokinetic and Pharmacodynamic Data

8.2.6.1 Analysis of Pharmacokinetic Data

PK parameters will be calculated from concentration data collected during the MAD phase 1b portion of the study using non-compartmental analysis and include the following:

- C_{max} , T_{max} , AUC, $t_{1/2}$, CL, V_d

The PK parameter data will be listed and summarized descriptively in tabular format.

If data permit, the following analyses will be performed for plasma BOS161721 concentration data:

- A listing of all plasma BOS161721 concentrations by patient at actual times post dose;
- A descriptive summary of plasma BOS161721 concentrations. Summary statistics of geometric mean, % coefficient of variation, standard deviation, median, minimum, and maximum will be tabulated by study days with PK assessments.

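### The single PK analysis set is tied to the efficacy FAS and to PK-parameter calculability, so it can exclude valid concentrations from summaries that need neither

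*Protocol*

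**What the plan says.** Protocol Section 8.2.1 names one population for all PK work: "Pharmacokinetic analysis will be conducted on the PK analysis set, defined as the FAS with sufficient concentration data for the calculation of PK parameters". Two conditions follow. The first comes from the FAS, whose members must have been dosed and must "have at least 1 evaluable post-baseline efficacy evaluation". The second is that the concentration data suffice to calculate PK parameters.

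Section 8.2.6.1 then plans two kinds of PK output. Parameters (Cmax, Tmax, AUC, half-life, clearance, volume) are "calculated from concentration data collected during the MAD phase 1b portion of the study". Separately, and not restricted to MAD, it plans a listing of plasma concentrations by patient and a descriptive summary by study day. Section 2.1 makes concentration by visit and time point a MAD secondary endpoint in its own right. Section 6.5 has PK blood taken at all sites in MAD and in the "POC phase 2 (select sites only) parts of the study".

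On treatment basis, Section 8.2.1 says "FAS analyses will be conducted on the basis of the randomized treatment" and "Safety analyses will be conducted on the basis of actual treatment received". It gives no basis for PK.

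**The concern.** A population for concentration data should depend on whether the patient received the drug and has a usable concentration. Neither condition in Section 8.2.1 does that. Having a SLEDAI-2K or BILAG assessment after baseline says nothing about whether a plasma sample is valid. Being able to estimate clearance or half-life is needed for a parameter table but not for a mean concentration at Day 15.

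This is not detail left to the analysis plan. The protocol fixes the rule. An analysis plan that followed it would discard valid data, and one that set it aside would contradict the protocol. At stake are the concentration summaries, including a MAD secondary endpoint in small dose groups. No efficacy conclusion is involved.

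**Working it through.** The protocol states no figure to reproduce here. The check sets the definition against the sampling schedules.

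**FAS condition.** In Tables 1 and 4 the first post-baseline efficacy assessments are at Day 30. PK samples due before then:

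- MAD (Table 4): predose, 4 h, 8 h, 24 h, Day 7, Day 15. That is 6 samples, 5 of them post-dose.
- POC, PK sites only (Table 1): predose and Day 15. That is 2 samples, 1 of them post-dose.

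A MAD patient who leaves before Day 30 and attends no later visit can therefore have 5 valid post-dose concentrations and still be outside the FAS, and so outside the PK set.

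**Size of that group.** Section 8.1 assumes 14 of about 110 POC patients drop out before treatment or before a post-baseline efficacy measure: 14/110 = 12.7%. At 2:1 allocation, 14 × 2/3 = 9.3, so about 9 on active drug. This is an upper bound, because some of the 14 are never dosed and POC PK is sampled only at selected sites. The protocol gives no comparable figure for MAD. Its active groups are 5, 9 and 9, so if one such patient occurred it would be 1/5 = 20% or 1/9 = 11% of a dose group.

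**Parameter condition.** The full POC schedule is 7 predose samples (Days 0, 30, 60, 90, 120, 150, 180) plus 6 post-dose samples (Days 15, 187, 195, 210, 240, 270), 13 in all. A patient followed to Day 270 has a 90-day profile after the last dose. Against the 80 to 87 day half-life in Section 1.2.2.3, that is 90/87 = 1.03 to 90/80 = 1.13 half-lives. A POC patient whose sampling ends after the Day 90 visit has 4 predose samples (Days 0, 30, 60, 90) and 1 post-dose sample (Day 15). Such data may well be judged insufficient for parameters, yet the concentrations at Days 15, 30, 60 and 90 are valid entries for the by-day summary. The definition removes them from a table that uses no parameter.

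**The case against.** The strongest reply is that the practical loss is small, and most of it stands.

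- Section 5.5 asks early withdrawals to attend an end-of-treatment visit and a final follow-up. The corresponding Day 180 and Day 270 columns include efficacy assessments, which can bring a patient back into the FAS. Exclusion needs departure before Day 30 and no later visit.
- Section 4.8.1 allows MAD withdrawals to be replaced.
- Samples to Day 15 span only 15/87 = 0.17 to 15/80 = 0.19 of a half-life, so an early leaver adds little to half-life, clearance or volume.
- Section 8 says all data are listed for all patients, and Section 8.2.6.3 names no analysis set for modelling. The loss therefore falls mainly on summary tables.

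These points limit the size. They do not make either condition suitable for a concentration summary.

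Two stronger readings are tempting, and the protocol does not support them. A reader might infer that the whole POC portion falls outside the PK set because parameters are planned only from MAD data. That merges two separate statements. Section 8.2.1 asks whether a patient's data suffice for parameters, whereas Section 8.2.6.1 says where parameters will be calculated. A POC patient with the full schedule is not plainly insufficient, and patients at non-PK sites have no samples to lose. A reader might also infer that concentrations are summarised under the randomised dose because the PK set is drawn from the FAS. The per protocol set is also drawn from the FAS, yet Section 8.2.1 gives it its own sentence on treatment basis. Inheritance therefore cannot be assumed. For PK the basis is unstated, which the analysis plan may settle.

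**Conclusion.** The point holds in a limited form. As written, Section 8.2.1 excludes from PK analysis a dosed and sampled patient with no evaluable post-baseline efficacy evaluation. It also excludes from the concentration summaries a patient whose data do not support parameter calculation. Neither exclusion has a PK rationale, and both conflict with what Section 8.2.6.1 plans.

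The number affected is probably small. The only protocol figure that bears on it is the 14 of about 110 assumed not to reach the FAS in POC, at most about 9 of them on active drug. How many further patients fail the parameter condition depends on how sufficiency is judged and on how many stop early, and the protocol gives neither. The outputs are descriptive; the primary endpoint, alpha and power are unaffected. The conclusion assumes that the PK set governs the concentration summaries as well as the parameters, which is the plain reading of a single set for pharmacokinetic analysis. It is worth correcting because the correction is almost free.

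**What to change.** Replace the PK sentence in Section 8.2.1 with two definitions:

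1. **PK concentration set:** patients in the safety set who received BOS161721 and have at least one evaluable post-dose concentration, in MAD or POC, summarised by actual treatment received as for the safety set. State that a sample taken before a second or later dose counts as post-dose with respect to the first.
2. **PK parameter set:** the subset of the concentration set with enough samples for the parameter in question, used for the non-compartmental analysis.

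Remove the reference to the FAS. In Section 8.2.6.1, assign the concentration summary to the first set and the parameter tables to the second, with matching wording in the analysis plan. The cost is a few sentences. No sample, visit or stated figure changes.

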8.2.2 Demographics and Baseline Characteristics

Baseline and patient characteristics will be summarized using all randomized patients.

8.2.3 Primary Efficacy Endpoint(s)

The proportion of patients who achieve a SRI-4 response at Day 210 will be assessed via Pearson's chi-squared analysis. The primary efficacy endpoint will be analyzed using the FAS and if needed repeated in the PP analysis set. Missing values will be addressed by employing a last observation carried forward (LOCF) analysis. Other imputation methods may be employed as a sensitivity analysis and will be described in the SAP. Analyses based on observed values may also be performed.

Exploratory subgroup analyses assessing impact of baseline factors such as baseline disease severity, background therapy, race, geography, baseline serologic activity and other characteristics may be performed. Additional exploratory analyses of disease activity endpoints may be performed based on emerging data.

Patients that received prohibited medications or unallowable CS usage as described in [Section 4.6](#) will be considered "medication failures" and will be treated as statistical non-responders at time points on or following the first date of prohibited medication or unallowable CS usage for the primary efficacy analysis. The determination of medication failures will be reviewed using blinded data and finalized prior to unblinding.

The superiority of BOS161721 relative to placebo will be evaluated. If the proportion of SRI-4 responders for the selected POC dose in BOS161721 arm is higher than that of the placebo arm, then BOS161721 will be considered superior to placebo if the 2-sided p-value is < 0.10 . Secondary and exploratory endpoints for this POC portion will be evaluated based on the same statistical hypothesis.

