3.2 Randomization and Blinding

This is a randomized, double-blind study.

Patients meeting all inclusion and exclusion criteria will be centrally randomized to either placebo or BOS161721 using an IWRS according to a randomization list generated by an independent, non-study statistician. Randomization will be performed separately for each study portion and separately for each cohort in the phase 1b and 2 portions as follows:

Phase/Cohort	Number of Patients	Randomization Ratio BOS161721:Placebo
Phase 1b/Cohort 1	6	5:1
Phase 1b/Cohort 2	12	3:1
Phase 1b/Cohort 3	12	3:1
Phase 2	Approximately 110	2:1

*Additional patients may be enrolled to ensure sufficient numbers of patients are in the full analysis set (FAS).

[figure not shown]
Eligible patients will be assigned to the study portion which is active at time of enrollment. Similarly, patients in the phase 1b MAD will be assigned to the cohort which is active. Each patient will be assigned a unique randomization number which will not be reused.

All patients, Investigators, and study team participants will be blinded to treatment assignment. An independent biostatistician not otherwise involved on the study will be unblinded and prepare materials for the IA, ad hoc analyses as needed, and the DMC

safety reviews. The DMC will review unblinded data during safety reviews and the IA. A limited team at Boston Pharmaceuticals will review unblinded results from the phase 1b MAD portion during the IA to determine the dose that will be used for the phase 2 POC portion of the study. Details regarding maintenance of the blinding and content of data reviews will be described in the DMC charter or related study documentation.

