8.2.4 Secondary Efficacy Endpoint(s)

Binary efficacy endpoints will be assessed via Pearson's chi-squared analysis. Continuous efficacy endpoints will be assessed via analysis of variance (ANOVA) or analysis of covariance (ANCOVA) and treatment will be compared using the F-test. Repeated measures mixed models may be performed to evaluate data collected at each visit and overall. Time-to-event endpoints will be assessed via Kaplan-Meier methodology and treatment will be compared using the log-rank test. The secondary efficacy endpoints will be analyzed on the FAS and if needed repeated in the PP analysis set. Details including handling of missing data and "medication failures" will be available in the SAP.

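### The primary SRI-4 test uses no baseline information; adjusting for SLEDAI-2K and Day 0 steroid dose would add about 0 to 8 points of power at almost no cost

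*Protocol*

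**What the plan says.** Protocol V7.0, Section 8.2.3, sets the primary test: "The proportion of patients who achieve a SRI-4 response at Day 210 will be assessed via Pearson's chi-squared analysis". The Protocol Summary (Statistical Considerations) and Section 8.1 name the same test. The sample size is "based on a targeted 2-sided significance level of 10% and using a 2-sided Pearson's chi-squared test", and Section 8.1 states that "A total of 96 evaluable patients randomized provides 80% power to detect a treatment difference of 29% in SRI-4 response rates at Day 210". No covariate or stratum is attached in any of the three places. Cochran-Mantel-Haenszel appears only in the list of abbreviations.

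On allocation, Section 3.2 says "Randomization will be performed separately for each study portion and separately for each cohort in the phase 1b and 2 portions". It gives 2:1 for phase 2 and lists no factor within that portion.

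Baseline severity and background therapy enter Section 8.2.3 only as optional exploratory subgroup factors. The opening of Section 8 says that covariate effects will be assessed, but gives no model and no link to the primary test.

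For other endpoints, Section 8.2.4 says "Continuous efficacy endpoints will be assessed via analysis of variance (ANOVA) or analysis of covariance (ANCOVA", with treatment compared by an F-test. The Protocol Summary is more specific: it plans ANCOVA, adjusted for the baseline value, where applicable.

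**The concern.** An SRI-4 response needs a fall of at least 4 SLEDAI-2K points (Section 6.3.4.1). Entry requires a screening score of at least 8 with no stated cap (Section 4.4), so the room to respond may differ between patients. Day 0 oral steroid may be anything up to 30 mg/day. Steroid increases outside the permitted ones make a patient a treatment failure (Section 4.6.1), and unallowable steroid use is scored as non-response (Section 8.2.3). Both variables are plausible predictors of the endpoint. Both are known before dosing, and the Day 0 dose is already needed for the steroid-reduction endpoints.

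With about 32 placebo patients, the arms can differ by chance on such a predictor. An unadjusted test cannot correct for that once it has happened, and it leaves unused any precision the predictor could supply. The trial turns on a single p < 0.10 decision, and a visible baseline imbalance with no prespecified adjustment would invite a post hoc argument about the result.

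**Working it through.** **Inputs from Section 8.1.** "This assumes a response rate of 62% for BOS161721 and 33% for placebo". "Approximately 110 additional patients will be randomized in a 2:1 ratio to BOS161721 versus placebo". "This assumes 14 patients will drop prior to having received treatment or having completed a post-baseline efficacy measure". Two-sided alpha is 0.10. The 96 evaluable patients at 2:1 are 64 active and 32 placebo. Dropout is 14/110 = 12.7%, and 96/(1 − 14/110) = 110.

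**1. The protocol's sample size.** Pooled rate = (0.33 + 2 × 0.62)/3 = 0.523, so p(1 − p) = 0.2495.
- Placebo n without continuity correction = [1.645 × √(1.5 × 0.2495) + 0.842 × √(0.2211 + 0.2356/2)]² / 0.29² = 26.6. This rounds to 27, or 81 in total.
- With continuity correction: (26.6/4) × [1 + √(1 + 6/(2 × 26.6 × 0.29))]² = 31.6. This rounds to 32, or 96 in total, so the stated figure reproduces.

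**2. Power of the named test at 64:32.** Null SE = √(0.2495 × (1/32 + 1/64)) = 0.1081. Alternative SE = √(0.2211/32 + 0.2356/64) = 0.1029.
- Uncorrected Pearson: z = (0.29 − 1.645 × 0.1081)/0.1029 = 1.09, power 86.2% (exact binomial enumeration: 85.8%).
- Continuity-corrected: power 80.6%.

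**3. Chance of imbalance.** SE of a standardised baseline difference = √(1/32 + 1/64) = 0.217. The probability of an imbalance of at least 0.2, 0.3 or 0.4 SD in one given covariate is 36%, 17% or 6%. For a yes/no factor held by half the patients, the SD of the between-arm difference is √(0.25 × (1/64 + 1/32)) = 10.8 points. An imbalance above 15 points then has probability 17%, and above 20 points 6%.

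**4. Effect of an imbalance on the observed difference.** Prognostic strength is not in the protocol, so it is assumed as an odds ratio (OR) per SD of one combined, normally distributed baseline score. Set response at 33% with no treatment effect, and centre the score at +d/3 in the active arm and −2d/3 in the placebo arm (difference d, pooled mean zero). With d = 0.3 SD, the response difference shifts by 2.6 points (OR 1.5), 4.1 points (OR 2) or 5.8 points (OR 3).

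**5. Effect of adjustment on power.** Simulation at 64:32 with 6,000 runs per row, marginal rates held at 62% and 33%, two-sided 0.10. CMH uses a median split of the score. The adjusted test is the likelihood-ratio test from logistic regression on treatment and the score. The SEs are for the response difference, unadjusted and standardised from the logistic model.

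| OR per SD | Pearson | CMH | Adjusted logistic | Gain over Pearson (points) | SE unadjusted → adjusted | Variance change |
|---|---|---|---|---|---|---|
| 1.0 | 86.4% | 86.0% | 86.4% | 0.0 | 0.103 → 0.103 | +1% |
| 1.5 | 85.0% | 85.4% | 86.6% | 1.6 | 0.104 → 0.103 | −2% |
| 2 | 84.6% | 87.3% | 88.6% | 4.0 | 0.104 → 0.099 | −10% |
| 3 | 85.9% | 90.0% | 92.2% | 6.3 | 0.104 → 0.094 | −18% |
| 4 | 85.2% | 91.0% | 93.4% | 8.2 | 0.104 → 0.090 | −25% |

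Simulation error is about √(0.86 × 0.14/6000) = 0.4 points. Under the null (33% in both arms), rejection rates were 9.9% to 11.1% for Pearson, 9.5% to 10.5% for CMH and 9.8% to 11.5% for the adjusted test. The 11.5% occurs at OR 4, so part of the gain in that row may reflect a slightly liberal test.

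**The case against.** The strongest reply is that nothing here is wrong. Pearson's test is valid, it is the test used for the sample size, and its power exceeds what the protocol claims. Chance imbalance is already part of its unconditional error rate. In a proof-of-concept trial, preferring an adjusted model is advice. All of this stands, and it rules out a reader's inference that the test is invalid or the trial underpowered.

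Other limits also stand:
- The 17% and 6% figures are chances of covariate imbalance. They are not shifts in the treatment effect. A 15-point imbalance in a yes/no factor moves the difference by 0.15 × 30 = 4.5 points only if that factor changes response by 30 points, which the protocol does not establish.
- Every patient must have a screening SLEDAI-2K of at least 8, so a 4-point fall is arithmetically possible for all. Steroid tapering is encouraged, not required. Both facts weaken any claim that these covariates must be strong predictors.
- The absence of stratification is read from a section that names no factor. The protocol does not say in words that phase 2 is unstratified.
- A reader might take Section 8.2.4 to mean that continuous endpoints will ignore baseline. The Protocol Summary contradicts that reading. ANOVA also has a proper use: duration of longest SRI-4 response has no baseline value.

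The reply that this can wait for the statistical analysis plan does not stand for the primary analysis. That plan could add an adjusted sensitivity analysis, but the protocol has already chosen the test that decides.

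**Conclusion.** The point holds as an improvement to a valid analysis. The primary test uses no baseline information although two relevant variables are in hand. The cost is lost efficiency and exposure to conditional bias if the arms happen to differ at baseline.

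The size depends wholly on the assumed prognostic strength: nothing is gained if the covariates do not predict response, about 1 to 2 points of power at an odds ratio of 1.5 per SD, and about 6 to 8 points at 3 to 4. The calculation treats the two covariates as one normally distributed score, and its power figures come from a likelihood-ratio test. The Wald test suggested below was not itself simulated, though the adjusted SEs point the same way. The change is worth making because it costs almost nothing and loses no appreciable power even when the covariates carry no information.

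**What to change.** Before unblinding:

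1. **Section 8.2.3.** Make the primary analysis a logistic regression of Day 210 SRI-4 on treatment, baseline SLEDAI-2K (continuous) and Day 0 prednisone-equivalent dose. Report the standardised risk difference with a 90% CI. The planned rates imply about 0.62 × 64 + 0.33 × 32 = 50 responders and 46 non-responders, which supports a model of this size.
2. **Decision rule.** Name one deciding two-sided p-value at 0.10, for example the Wald test of the standardised risk difference, and fix its standard error (delta-method or robust). The tests of the logistic coefficient and of the risk difference can disagree near 0.10, so the choice must be made in advance.
3. **Supportive analysis.** Keep Pearson's chi-squared test. The sample size in Section 8.1 can stay, with a sentence saying that it rests on the unadjusted test. Align the Protocol Summary.
4. **Section 8.2.4.** Carry over the Protocol Summary's baseline-adjustment wording so that every change-from-baseline endpoint uses ANCOVA, or the mixed model, with its baseline value. Keep ANOVA only for endpoints without a baseline, such as duration of longest SRI-4 response.

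The cost is a few lines of text. No new data, visits or patients are needed.
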